# 5.2 Post-Surgery/Adjuvant Therapy

 Includes weight, BSA, and vital signs (temperature, blood pressure, pulse rate, and). Following the initial presurgery dose, for subsequent doses, the post dose vitals and 1-hour observation period will not be required unless a subject experiences an infusion-related reaction. Vital signs will be measured within an hour prior to start of study drug administration, at 30 minutes during the infusion (± 5 minutes), at the end of infusion (+ 5 minutes). If needed, vital signs will be done at 30 and 60 minutes (± 5 minutes each) post-infusion. If the infusion takes longer than 60 minutes, blood pressure and pulse measurements should follow the principles described here or more frequently if clinically indicated.

 Adjuvant treatment (cycle 1 day 1) will resume approximately 14 days (+/- 7 days) after surgery, once the surgical wound has healed.

 Will be done every other week while on adjuvant treatment.

 Will be done prior to each cycle (monthly) while on adjuvant treatment.

 If patients are unable to start treatment within 21 days of the post-surgical imaging, then repeat imaging with

enhanced MRI or CT scan should be performed prior to initiation of adjuvant therapy. During adjuvant treatment, contrast-enhanced MRI or CT scan will be done approximately every 2 cycles or 8 weeks (prior to each odd cycle). If there is no progression of disease, patients will continue on treatment for up to 24 months. If a patient has disease progression (as defined in section 6.4) or clinical decline and undergoes further surgery but is found to have no pathologic evidence of significant tumor, the patient may then re-start treatment.

-  Thyroid function tests will be done every 2 cycles (approximately every 2 months) during treatment. TSH will be done each time; free T3 and free T4 only if TSH is abnormal.
-  ECGs are required within 1 hour prior to starting study treatment and at least once after the infusion is completed (anywhere from 0-3 hours) on Cycle 1 Day 1, again after approximately 16 weeks on treatment, and at the end of treatment. ECGs may be repeated at any other time point if clinically indicated. ECGs recorded during the treatment phase will be single tracing. Twelve-lead ECGs will be obtained after the subject has been resting in a supine position for at least 5 minutes in each case.
-  During adjuvant treatment, one cycle is defined as 4 weeks for patients on Arms 1 and 2. For patients on Arm 3, please refer to the schedule outlined in footnote #14.
-  Blood samples will be collected for various research tests at 1 st pre-operative treatment, day of surgery, C1D1 and at each adjuvant treatment imaging visits (i.e. every 2 cycles or 8 weeks):
  - a) 10ml blood in one 10ml Sodium heparin tube: To be collected and processed by the [name] lab for peripheral blood lymphocytes (PBLs).
  - b) 8m (2x4ml) blood in two 5ml EDTA (purple top) tubes: To be collected and processed by the [name] lab for gene expression profile using mononuclear cells.
  - c) 10ml blood in one 10ml red top tube: To be collected and processed by the [name] lab for analysis of tryptophan catabolites and cytokines.
  - Please refer to section 9.0 and laboratory manual for more details
-  Any patient who undergoes further surgery will have the option to use their tumor tissue for research to understand the immunologic changes occurring at the time of presumed drug failure. Please refer to Section 9 and laboratory manual for details.
-  Follow up for disease progression (if not already documented) and survival will occur every 8-16 weeks once off treatment. All patients will be followed until death or 2 years/24 months from stopping treatment.
-  Patients enrolled on Arm 1 will receive tremelimumab monotherapy: one 75 mg dose IV on day 1 (+/- 2 days) per cycle (every 4 weeks) up to 24 months.
-  Patients enrolled on Arm 2 will receive MEDI4736 monotherapy: one 750 mg dose IV on days 1 and 15 (+/- 2 days allowed for each) per cycle (every 2 weeks) up to 24 months.
-  Patients enrolled on Arm 3 will receive combination therapy (tremelimumab 75 mg + MEDI4736 750 mg) according to the following schedule: Tremelimumab will be administered IV every 4 weeks (Day 1 of each cycle) and MEDI4736 750mg every 2 weeks (Day 1 and Day 15 of each cycle) until the patients have received 7 doses of Tremelimumab and 14 doses of MEDI4736. Thereafter, from Cycle 7 (Week 25), Tremelimumab will be given every 12 weeks (+/-7 days) and MEDI4736 will be given every 2 weeks (+/- 2 days) until permanent discontinuation criteria (e.g. disease progression) is met. If there is no progression of disease, they will continue on treatment for up to 24 months.

# 6.0 ENDPOINT ASSESSMENT

## 6.1 **Primary Endpoint**

To determine the T-cell changes (immunologic changes) that occur in recurrent GBM treated with Tremelimumab and MEDI4736 as single agents and in combination. The changes from baseline will be assessed in blood samples and tissue samples before treatment and post-surgery for all patients in the 3 arms. A comparison between the changes observed in the 3 arms will be made.

Only patients who have had pre-treatment blood sampling, have undergone surgery with pre-surgical blood sampling, and are able to continue to post-operative drug treatment with blood sampling prior to the first post-surgical dose will be evaluable for this endpoint.

### 6.2 Secondary Endpoints

- 1. To evaluate the safety of either Tremelimumab or MEDI4736 alone and in combination for patients with recurrent GBM. The endpoints will be the number, frequency, and severity of adverse events (as defined by the NCI Common Terminology Criteria for Adverse Events or CTCAE version 4.03). Only patients who have been administered at least one dose of investigational drug will be evaluable for this endpoint.
- 2. To determine post-surgery, the time to progression (per Modified RANO criteria and iRANO criteria see below) for patients treated with either Tremelimumab or MEDI4736 alone and in combination of both. This will be defined as the number of months from the time of first dose of study treatment until progression of disease or death by any cause. Only patients who have been administered at least one dose of investigational drug and undergone surgery will be evaluable for this endpoint.
- 3. To determine post-surgery the overall survival for patients treated with Tremelimumab or MEDI4736 alone and in combination of both. This will be defined as the number of months surviving from the time of first dose of study treatment until death by any cause. Only patients who have been administered at least one dose of investigational drug and undergone surgery will be evaluable for this endpoint.
- 4. To assess post-surgery, the MRI changes in patients treated with either Tremelimumab or MEDI4736 alone and in combination of both. Only patients who have been administered at least one dose of investigational drug, undergone surgery, and have undergone at least one post-surgery disease assessment will be evaluable for this endpoint.

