## 2.2 Secondary Objectives & Endpoints

- 2.2.1 To evaluate the safety of either Tremelimumab or MEDI4736 alone and in combination in patients with recurrent GBM. The endpoints will be the number, frequency, and severity of adverse events (as defined by the NCI Common Terminology Criteria for Adverse Events or CTCAE version 4.03).
- 2.2.2 To determine post-surgery, the time to progression(per Modified RANO criteria and iRANO criteria see below) for patients treated with either Tremelimumab or MEDI4736 alone and in combination of both, This will be defined as the number of months from the time of first dose of study treatment until progression of disease or death by any cause.
- 2.2.3 To determine post-surgery the overall survival for patients treated with Tremelimumab or MEDI4736 alone and in combination of both. This will be defined as the number of months surviving from the time of first dose of study treatment until death by any cause.
- 2.2.4 To assess post-surgery, MRI changes in patients treated with either Tremelimumab or MEDI4736 alone and in combination of both.

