## **3.0 PATIENT ELIGIBILITY**

The target population for this study is patients with recurrent glioblastoma. This will be a single-center trial conducted at neuro-oncology clinic of Northwestern University.

A total of 30 evaluable subjects will be needed for this trial. The accrual cap is 45 patients, in order to cover those patients that do not make it to the first evaluable time point. Hence, the total accrual per arm will be up to 15. Approximately 4 potentially eligible patients are seen per month, and it is anticipated that at least 2 per month will be accrued. Potential patients may be referred to the Principal Investigator (PI) at Northwestern University, [name], at [contact].

Eligibility will be evaluated by the study team according to the following criteria. Eligibility waivers are not permitted. Subjects must meet all of the inclusion and none of the exclusion criteria to be registered to the study. Study treatment may not begin until a subject is registered.

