## 4.0 TREATMENT PLAN

## 4.1 Overview

Patients will be treated with either Tremelimumab 75 mg alone, MEDI4736 750 mg alone, or both in combination. Patients will be randomly allocated using block randomization to ensure equal sample sizes per arm. Up to 45 patients (15 per arm) will be randomized to ensure that 30 patients are evaluable for immunologic response (10 per arm).

Patients will then undergo a surgical resection of their tumor that is part of their medical care 2 weeks later to remove the tumor. Two weeks is expected to be enough time for immunologic changes to occur in the tumor. Standard pre-surgical testing will be done prior to surgery. At the time of surgery, tissue will be removed for local pathology review and send to [name] for evaluation (see Section 9.0 for details).

Post-operative care will be standard for patients who undergo a craniotomy and tumor resection at NMH. Patients will have a standard post-operative MRI or CT scan of the brain within 72 hours of surgery. Following surgery, patients will resume treatment on the same regimen they were assigned to receive before surgery. Treatment may continue until disease progression or unacceptable toxicity.

Treatment Administration Summary					
Arm	Treatment	Dose	Route	Schedule	Supportive Therapies**
1	Tremelimumab monotherapy	75 mg	IV at 250ml/hr	Once within 14 d (+/-3) pre-surgery. Adjuvant: Every 4 weeks	Acetaminophen and/or antihistamine or equivalent 
2	MEDI4736 monotherapy	750 mg	IV over 60min+/-5 mins 	Once within 14 d (+/-3) pre-surgery. Adjuvant: Every 2 weeks	Acetaminophen and/or antihistamine or equivalent 

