-  Patients will receive one dose of tremelimumab 75 mg (if on Arm 1), MEDI4736 750 mg (if on Arm 2) or the combination of both (if on Arm 3) approximately 2 weeks (14 days +/- 7 days) before surgery.
-  Tumor from prior surgeries will be requested on all patients. Tissue will be analyzed in the [name] Laboratory. Please refer to Section 9.3 and laboratory manual for details.
-  Blood samples will be collected for various research tests at 1 st pre-operative treatment, day of surgery, C1D1 and at each adjuvant treatment imaging visits (i.e. every 2 cycles or 8 weeks):
  - a) 10ml blood in one 10ml Sodium heparin tube: To be collected and processed by the [name] lab for peripheral blood lymphocytes (PBLs).
  - b)8m (2x4ml) blood in two 5ml EDTA (purple top) tubes: To be collected and processed by the [name] lab for gene expression profile using mononuclear cells.
  - c) 10ml blood in one 10ml red top tube: To be collected and processed by the [name] lab for analysis of tryptophan catabolites and cytokines.

Please refer to section 9.0 and laboratory manual for more details

 Chemistries should include electrolytes, calcium, , albumin, alkaline phosphatase, bilirubin (total), SGPT(ALT), SGOT(AST), serum creatinine, and BUN.

 TSH, T4, T3

 Required at baseline only but may be repeated as clinically indicated thereafter.

 Includes hepatitis A antibody, hepatitis B (HBsAg reactive), and Hepatitis C (HCV RNA [qualitative] detection).

 Please refer to Section 9.1 and the laboratory manual for details.

Time Period	Adjuvant Treatment 		Off Treatment			
Assessment/Activity	Cycle 1 Day 1  (+/- 2d)	Cycle 2 Day 1 (+/- 2d)	Cycle 3+ Day 1 (+/- 2d)	Treatment Discontinuation	90 Days Post Last Dose (+/- 7d)	Follow-up 
Concomitant medications	X	X	X			
Toxicity assessment	Х	Х	X	X	X	
Neurological exam and KPS 	Х	X	X	Х	Х	
Vital signs & weight 	X	X	X			
CBC with diff 	X		X	X	Х	
Comprehensive Chemistry Panel	X	X	X	X	Х	
Thyroid Function Tests 	X		X	X	Х	
ECG 	X			X		
Tumor Imaging (MRI/CT)	X 		X 	X 		
Tremelimumab monotherapy 	Х	X	X			
MEDI4736 monotherapy 	X	X	X			
Combination therapy 	X	X	X 			
Research tissue		X 	·			·

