# 6.4 Response Assessment (Modified RANO criteria)

The response to immunotherapy may differ from the typical responses observed with cytotoxic chemotherapy including the following (Wolchok et al 2009, Nishino et al 2013):

- Response to immunotherapy may be delayed
- Response to immunotherapy may occur after PD by conventional criteria
- The appearance of new lesions may not represent PD with immunotherapy
- SD while on immunotherapy may be durable and represent clinical benefit

Based on the above-described unique response to immunotherapy and based on guidelines from regulatory agencies, e.g., European Medicines Agency's "Guideline on the evaluation of anticancer medicinal products in man" (EMA/CHMP/205/95/Rev.4) for immune modulating anticancer compounds, the study use a modified RANO criteria to define PD:

Progressive disease post-baseline is defined as one or more of the following:

- New contrast-enhancing lesion outside of radiation field on decreasing, stable, or increasing doses of corticosteroids.
- Increase by > 50% (modified from >25% according to published RANO criteria) enhancement from the first post-surgical scan, or a subsequent scan with smaller tumor size, and the scan 8 weeks or later on stable or increasing doses of corticosteroids.
- Clinical deterioration not attributable to concurrent medication or comorbid conditions is sufficient to declare progression on current treatment.

Treatment with MEDI4736, Tremelimumab or both would continue between the initial assessment of progression and confirmation for progression. In addition, subjects may continue to receive MEDI4736, Tremelimumab or both beyond confirmed PD in the absence of clinically significant deterioration and if investigators consider that subjects continue to receive benefit from treatment.

As a secondary measure, for all response assessments, iRANO will be used for assessment.

RANO and iRANO criteria (iRANO= immunotherapy Response Assessment in Neuro-Oncology)						
	Response	Malignant glioma	Low-grade glioma	Brain metastasis		

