#### 10.3 Sample Size, Accrual and Data Analyses Plans

There will be three groups of patients, one group on each agent alone and one group treated with the combination agent. There will be 10 patients per group for a total of 30 patients. These 30 patients must be evaluable for the primary endpoint, meaning that they must have undergone surgery and their blood and tissue samples are available at both the pre- and post-surgery times. In order to attain 10 evaluable patients in each arm, a total of 45 patients will be accrued to the study. Sample sizes of 10 per group allow for the estimation of the proportion of responders in evaluable patients to be within 31% of its true value with 95% confidence. Mean change will be compared between arms. Using standard deviations of change, a sample size of 10 per group will allow the detection of differences of 1.25 standard deviations between groups with 80% power assuming a two-tailed test and a Type I error rate of 5%.

Immunologic measures will be summarized over the three or more time points (pre-treatment, following first treatment/pre-surgery, post-surgery) and changes in these measures will be assessed using repeated measures analysis of variance or Cochran's Q, followed by the paired t-test or the signed rank test for pairwise comparisons using Bonferroni corrections. Safety of the agents alone or in combination will be assessed by summarizing the frequency of adverse events by type, timing, grade and attribution. Response criteria will be based on RANO (including upcoming Immunologic RANO criteria) but since all patients will be post-surgery, the degree, if any, of

residual disease will vary. A patient is evaluable for efficacy if they have undergone at least one follow-up MRI after adjuvant therapy. Immunologic changes will be correlated with MRIs in a descriptive fashion. The secondary endpoint of progression-free survival as well as overall survival will be analyzed using Kaplan-Meier curves. Immunologic changes of T-cells and PDL1 levels will be correlated to survival outcomes using Cox regression analysis. MRI changes will be summarized using means or proportions and statistically analyzed using the signed rank test.

**Performance Status:** Patients will be graded according to Karnofsky Performance Status (KPS)(see appendix C).

**Evaluation of toxicity.** All patients will be evaluable for toxicity from the time of their first treatment as per NCI CTCAE version 4.03

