**Time to Progression:** From date of first treatment to the date of first observation of definitive progressive disease, non-reversible neurologic progression or increasing steroid requirements (applies to stable disease only), death due to any cause, or early discontinuation of treatment. Patients not reaching the progression endpoint at last follow-up will be censored at that time.

**Time to Death**: From date of first treatment to date of death due to any cause. Patients alive at last follow-up will be censored at that time.

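### Time to progression and OS start at the pre-surgical dose but count only operated patients, and Sections 6.2 and 10.3 disagree on population and progression events

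*Combined protocol and SAP*

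**What the plan says.** **Time origin.** Sections 2.2, 6.2 and 10.3 all start both clocks at the first dose. For OS, Section 2.2.3 says: "This will be defined as the number of months surviving from the time of first dose of study treatment until death by any cause". The objectives themselves are framed as post-surgery outcomes.

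**Population.** For both endpoints Section 6.2 says: "Only patients who have been administered at least one dose of investigational drug and undergone surgery will be evaluable for this endpoint". The definitions of Time to Progression and Time to Death in Section 10.3 carry no surgery condition. Section 10.3 separately makes efficacy evaluability depend on a follow-up MRI after adjuvant therapy, without saying which endpoints that governs.

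**Method.** "The secondary endpoint of progression-free survival as well as overall survival will be analyzed using Kaplan-Meier curves" (Section 10.3).

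**Progression events.** Section 6.2 counts progression or death. Section 10.3 lists definitive progression, irreversible neurological worsening and then "increasing steroid requirements (applies to stable disease only), death due to any cause, or early discontinuation of treatment". Section 6.4 defines progression by a new enhancing lesion outside the radiation field, clinical deterioration, or an increase of more than 50% in "enhancement from the first post-surgical scan, or a subsequent scan with smaller tumor size".

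**Dose-to-surgery interval.** The treatment table in Section 4 gives "Once within 14 d (+/-3) pre-surgery"; Section 5.1, footnote 6, gives "approximately 2 weeks (14 days +/- 7 days) before surgery".

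**The concern.** Section 6.2 takes its clock from one design and its population from another. Membership of the analysis set depends on surgery, which happens after time zero. Every included patient has therefore survived to surgery, and a dosed patient who dies first appears in neither curve. Deaths of dosed patients who are never operated on are also lost from OS. A plain Kaplan-Meier curve from first dose does not correct for this.

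The wording of Section 10.3 would let another analyst include all dosed patients, or only those with a follow-up MRI. The event lists add a second ambiguity: a patient who stops treatment for toxicity without progression is an event under 10.3 and still at risk under 6.2.

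At stake are the medians and rates reported per arm. The same times also feed the Cox regressions on T-cell and PD-L1 changes (10.3) and the responder grouping in Section 9.2.

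**Working it through.** **1. The plan's own figures.** The documents give no event count, median or hazard ratio for these endpoints. The only power statement concerns the primary endpoint: 1.25 × √(10/2) − 1.96 = 0.835, which is 79.8% power by the normal approximation and agrees with the stated 80%. Nothing below changes it.

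**2. Shift of origin** (month = 30.44 days). Planned interval: 14/30.44 = 0.46 month. Under ±3 days: 11 to 17 days, 0.36 to 0.56 month. Under ±7 days: 7 to 21 days, 0.23 to 0.69 month. If every operated patient has the same interval L, the first-dose curve is the surgery-origin curve moved right by L.

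**3. Selection through pre-surgery deaths.** Let k of 15 dosed patients in an arm die before surgery (15 is the per-arm cap in Section 3.0; k is assumed). With q = k/15, after surgery S_all(t) = (1 − q) × S_operated(t), so inflation is 15/(15 − k).

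- k = 1 gives 15/14 = 1.07. An operated-set survival of 50% corresponds to 0.50 × 14/15 = 46.7% in all dosed.
- k = 2 or 3 gives 1.15 or 1.25. With a constant hazard over 14 days, the implied median is ln2 × 0.46 / ln(15/(15 − k)): 4.6 months for k = 1, 2.2 for k = 2, 1.4 for k = 3. Section 3.1 requires life expectancy of at least 12 weeks (84/30.44 = 2.8 months), KPS of at least 70 and resection candidacy, so k = 2 or 3 is hard to square with eligibility.
- For assumed medians of 6, 9 and 12 months, 45 × (1 − exp(−ln2 × 0.46/median)) gives 2.3, 1.6 and 1.2 expected deaths over all arms, under one per arm.

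**4. Selection through living, unoperated patients.** OS is overstated by q × (S_operated − S_unoperated). One of 15, with an assumed gap of 20 or 40 points, gives 1.3 or 2.7 points. With no gap it is zero.

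**5. Scale.** The 95% half-width for a 50% proportion with 15 patients is 1.96 × √(0.25/15), about 25 points.

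**6. The MRI rule, if applied here.** A patient would need to reach roughly 14 + 14 + 56 = 84 days, or 2.8 months, from first dose (first dose to surgery, surgery to restart, first 8-week scan). With ±7 days on the first two intervals the range is 70 to 98 days, 2.3 to 3.2 months.

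**7. Event lists side by side.**

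| Item | 6.2 | 10.3 | Progression by itself in 6.4? |
|---|---|---|---|
| Progressive disease | yes | yes | yes |
| Neurological worsening | through progression | yes | yes, as clinical deterioration |
| Rising steroid need in stable disease | no | yes | no |
| Stopping treatment early | no | yes | no |
| Death | yes | yes | not applicable |

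In the modified criteria, steroid dose only qualifies the imaging items. The RANO table makes non-increasing steroids a condition for stable disease and marks steroids as not applicable for progression. Sections 4.6 and 5.2 (footnote 11) keep following patients for disease after a non-progression discontinuation.

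As an illustration only, assume a median of 3 months to progression or death and independent exponential discontinuation with a median of 6, 12 or 24 months. The composite median is 1/(1/3 + 1/m) = 2.0, 2.4 or 2.7 months.

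**The case against.** The best defence is that first dose is an explicit origin, used consistently, and the pre-surgical dose is part of the regimen. Restriction to operated patients fits objectives framed as post-surgery. The shift is the same planned interval in every arm, deaths within two weeks should be rare in this population, and any selection effect is small beside a ±25-point half-width.

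Much of this stands. A reader might take the 0.46 month as survival bias built into the medians. It is not: against a first-dose target it is simply the chosen origin, and it is a discrepancy only against the post-surgery objective. A reader might also say the whole plan discards pre-surgery deaths. Section 6.2 does, but the definitions in 10.3 do not, so the population is inconsistent rather than uniformly restricted. Nor is freedom from progression guaranteed up to surgery: an operated patient could already have a new lesion or clinical deterioration under 6.4.

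The steroid item has a plausible source in the RANO condition for stable disease, but that does not make rising steroids a progression event in 6.4.

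What the defence does not answer is the pairing. If the operated set is intended, the clock should start at surgery; if first dose is intended, all dosed patients belong in the analysis.

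**Conclusion.** The point holds as a mismatch of clock and population in 6.2, an unresolved population between 6.2 and 10.3, and conflicting time-to-progression events. The event-list conflict rests on the text alone.

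First-dose curves in operated patients are biased upward for certain if any dosed patient dies before surgery, and for OS also if unoperated survivors fare worse. The amount cannot be fixed from the documents and is zero if all dosed patients reach surgery. One pre-surgery death of 15 gives a factor of 1.07; more than that from deaths alone is unlikely given eligibility.

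The accrual allowance should not be read as the size of the loss. Section 3.0 says: "The accrual cap is 45 patients, in order to cover those patients that do not make it to the first evaluable time point". That is 15 of 45 for the primary endpoint, and it also covers operated patients who do not restart treatment.

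Nor do the documents support a claim of a distorted arm comparison. No between-arm survival test is planned, and arms would differ in bias only if the share operated on, or the interval, differed. The matter should be corrected, but it affects secondary descriptive estimates and leaves the planned sample size untouched.

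**What to change.** 1. For the operated set, start both clocks at surgery. Exclude from the time-to-progression landmark analysis any operated patient who already met a Section 6.4 criterion before surgery. Report these patients, and all pre-surgery deaths and discontinuations, by arm.
2. Also report OS from first dose in all dosed patients by assigned arm, using the follow-up already planned in Sections 4.6 and 5.2. Censor at last contact those who withdraw consent or leave follow-up for another study. Any all-dosed time-to-progression analysis should be a sensitivity analysis, because unoperated patients have no post-surgical reference scan.
3. State in Section 10.3 that the follow-up-MRI rule does not restrict OS or time to progression.
4. Use one time-to-progression event list in 6.2 and 10.3. Do not count a non-progression discontinuation as an event, and reconcile the steroid item with the RANO table and the modified criteria in 6.4.
5. Reconcile the two dose-to-surgery windows (±3 and ±7 days).

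The cost is wording in Sections 2.2, 6.2 and 10.3 plus minor programming, with no new data collection. Operated-set medians become about 0.46 month shorter, and a few patients in the all-dosed OS analysis will be censored early.
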